In this regard, evidence-based approaches, such as strengths-based care management, could be added to BIs to enhance efficacy; however, to be feasible in the ED and VHA, service delivery needs to be modified to minimize demands on VHA providers. Peers are ideal candidates for providing alcohol BIs and post-ED strengths-based assistance in the form of peer mentoring because of their shared experiences with patients. Peers can serve as role models and provide emotional support resulting in greater self-efficacy, healthy behavior change, and linkage to needed services.^{9,10} *Therefore, the objective of this proposed study is to conduct a hybrid randomized controlled trial (RCT) to determine the efficacy of an peer-delivered alcohol intervention starting in the ED with peer-delivered brief alcohol advice, combined with a continuing 6-session program of post-ED strengths-based peer mentorship, compared to standardized brief advice in the ED only, to facilitate reduction in risky drinking and linkage and engagement in primary and/or specialty alcohol treatment services care, if needed – an **Alcohol Peer-Mentor Intervention (APM; n=225)**, compared to **Brief Advice in the ED only (BA; n=225)** condition. The primary specific aims are to:*

Aim 1: Determine the efficacy of the ED APM intervention compared to BA on subsequent TLFB drinking frequency reports, including number of drinking days per month, number of drinks per drinking day, and number of binge drinking days at 3-, 6-, and 12-months post-baseline. **Hypothesis:** Veterans with hazardous drinking who are randomly assigned to APM will have significantly greater reductions in alcohol use as measured by TLFB reports, compared to those assigned to BA at 3-, 6-, and 12-month follow-ups.

Aim 2: Determine the impact of the APM intervention on linkage to primary and specialty alcohol treatment services care, mental health symptoms and functioning at 3-, 6-, and 12-months post-baseline. **Hypothesis:** Veterans with hazardous drinking who are randomly assigned to APM will be significantly more likely to link and engage in primary, specialty care, and other VHA supportive services and to have improvements in mental health symptoms and functioning.

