Measures (see Table 2 for measures and timing). The screen (~10 minutes) will be completed on paper by participants and will include demographics and the 10-item Alcohol Use Disorders Identification Test (AUDIT). Veterans screening positive on the AUDIT-C (4+ men/3+ women) will be consented to participate in the study. The baseline (~45 minutes) will be completed as an in-person interview in the ED and recorded on paper forms by RA. Participants may have the option to complete the baseline alone on paper-form or on the phone within up to two-weeks after enrollment, if necessary. Follow-up assessments will be completed over the phone (or in person if necessary) and responses will be entered into VA REDCap in real-time.

Screening Measure

The Mini-Cog assessment will be administered to all potential participants to detect cognitive impairment and inability to consent. A score of 3 or more will indicate no sign of cognitive impairment, therefore patient will be eligible for recruitment and screening.

Primary Outcome

Alcohol Consumption. We will administer a 30-day Timeline Follow-back (TLFB) for finer grained data (e.g., average consumption, percent days drinking, binge drinking days) (Hoeppner et al., 2010)⁹⁶

Secondary Outcomes

Alcohol Consumption: We will administer the AUDIT which includes the 3 questions of the AUDIT-C^{64,65,97} assessing alcohol consumption and binge drinking over the past 3-months, and 7 consequence questions, with established reliability and validity.^{65,66} In addition to standard item responses (e.g., categorical), we will enhance responses to obtain exact numbers for data analyses purposes to produce continuous response scales. Inclusion criteria are scores of 3+ for women and 4+ for men. A recent study validates the full AUDIT among Veterans, with scores of 14 and 10 (male, female, respectively) indicating an AUD.⁵⁶ However, to be inclusive, we will set the score for recommending specialty care conservatively at 10 for men and 8 for women.

Alcohol Consequences. The Short Index of Problems (SIP) will be used to assess drinking consequences with adequate reliability and validity.

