Data Management. The project's data manager will conduct all data management and analysis activities under the supervision of Drs. [name] and [name]. Research staff will use double entry procedures and reconcile discrepancies. Data cleaning will be conducted throughout data collection to ensure a quality final dataset for analysis. Statistical Analysis System (SAS) will be used to examine and prepare data for the analysis.

General analytic approach. Hypotheses will be planned a priori, and will be limited to the examination of a limited number of outcomes. We will utilize an "intent-to-treat" approach. All analyses will use two-sided tests because it is possible that the APM participants might have worse outcomes compared to CBA participants. Analyses will begin with descriptive data analyses to determine distributions of key variables, to collapse categories, if necessary, and to review data for outliers and clear anomalies. Tests for linearity, independence, missingness, and distributional assumptions will also be performed. Normalizing transformations of the dependent variables will be utilized, if necessary. We will validate the randomization scheme by comparing the initial groups on key variables that could be associated with the outcomes. Where we identify significant differences between groups, we will adjust for these variables, as well as other addictions treatment received if it was not initiated by referral from the APM or CBA clinician (and thus a potential mediator of effect). Prior to fitting any analytic models, a graphical exploration of the outcome variables will be conducted to select the appropriate models based on variable distributions.

Missing data. Every effort will be made to minimize missing data. Where we have missing covariates that are necessary for analysis, we will perform multiple imputation of missing data and combine the results from 5 imputations based on Rubin's method to produce an estimate and the corresponding confidence interval accounting for missing data uncertainty.⁸⁸ For follow-up attrition, the proposed mixed-effects regression model will allow the use of data from all participants (not just those with complete follow-up) and provide unbiased

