parameter estimates that account for missing data under the missing-at-random assumption.⁸⁹ We will look for non-random attrition, and if we find, for example, attrition rates to depend on a baseline covariate, we will include this covariate in the model. If we find attrition to depend on treatment use or ideation at prior assessments, we will utilize an appropriate pattern mixture model or multiply impute data based on an appropriate pattern mixture model assumptions based on the observed missing data pattern.⁸⁸

Aim 1: Determine the efficacy of the ED APM intervention compared to BA on TLFB drinking frequency reports at 3-, 6-, and 12-months post-baseline. **Hypothesis:** Veterans with hazardous drinking who are randomly assigned to APM will have significantly greater reductions in total TLFB drinking frequency reports, compared to those assigned to CBA.

Data Analysis for Aim 1: The primary purpose of Aim 1 is to examine the impact of the intervention on frequency of drinking per TLFB interview. This outcome will likely follow the assumptions required for linear regression model, but we will adjust the model type as needed. Assuming this is the case; we will use a linear mixed-effects model and estimate the treatment effect as the difference in the time-averaged TLFB frequencies over the year of follow-up. Because reduction in problem alcohol use is of primary interest, the analysis will model change-scores from baseline in the response variable as dependent variable, and the independent variables will include the baseline values of the response variable, time in months since randomization, and the treatment group indicator. The parameter estimate of the treatment group indicator will estimate the time-averaged treatment effect. *In a second model, we will include an interaction of time by treatment group indicator to formally test the possibility that the effect varies over time. Models will include a random effect for which specific peer/clinician a participant was assigned.*

Aim 2: Determine the impact of the APM intervention on linkage to primary and specialty alcohol treatment services care, mental health symptoms and functioning at 3-, 6-, and 12-months post-baseline, compared to BA. **Hypothesis:** Veterans with hazardous drinking who are randomly assigned to APM will be significantly more likely to engage in primary, specialty care, and other VHA supportive services and to have improvements in mental health symptoms and functioning.

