Data Analysis for Exploratory Aim: Interviews will be audiotaped and transcribed verbatim for content. We will conduct analyses. We will use a rapid data analysis process, a technique used when there is a need for targeted, actionable information.⁹³ The research team will read early transcripts independently, and, in an iterative process, meet to develop and refine the coding scheme and code definitions, including developing new codes from the data based on ongoing data analysis. We will document code definitions, data interpretation, and analytic decisions in memos. Once the research team has agreed on codes and code definitions, Drs. [name] and [name], and the research supervisor, will independently review and code transcripts, meeting regularly to compare coding results, and resolving discrepancies through a consensus process. If coding definitions are refined during this process, the coders will recode transcripts already coded. Once data are coded, we will use QSR NVivo 10 software to organize the data. The study team will meet regularly to discuss code summaries and memos, developing findings with a focus on barriers and facilitators to implementation and potential testable implementation strategies. Members of the study team have used similar methods in a study of the acceptability of peer support interventions in Michigan NG soldiers.^{94,95}

Power and Sample Size Calculations

Of 450 participants randomized, we expect that at least 80% of participants will be retained (n=360). We conservatively have estimated power without accounting for methods that will allow inclusion of participants with partial follow-up data because this benefit will be off-set to an unknown degree by the additional parameters estimated in a mixed effects model. All power analyses used G*Power 3.1.9 software and a two-sided $\alpha = .05$. We calculated power based on several potential outcome measure distributions. If a linear model is appropriate, which we expect to be the case for the primary outcome of total AUDIT scores, we achieve 80% power to detect an effect size (Cohen's d) of 0.30. This is a relatively modest and reasonable effect size for studies of SBIRT models of alcohol brief interventions. For an outcome with a count distribution and assuming a mean level in controls of 1 (e.g., an average of 1 alcohol-related treatment visit in a follow-up period), we achieve 80% power to detect an incidence rate ratio of 0.75 or 1.34 under a Poisson framework.

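### No single primary TLFB measure or success rule is fixed, and the power statement names the AUDIT, which the plan elsewhere lists as secondary

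*Combined protocol and SAP*

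**What the plan says.** All references are to the combined protocol and SAP.

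**Which instrument is primary.** Under Measures, Primary Outcome, the entry is: "We will administer a 30-day Timeline Follow-back (TLFB) for finer grained data (e.g., average consumption, percent days drinking, binge drinking days". The AUDIT ("We will administer the AUDIT which includes the 3 questions of the AUDIT-C") and the consequences scale ("The Short Index of Problems (SIP) will be used to assess drinking consequences") both come under Secondary Outcomes, and Table 2 agrees. Two later places differ. Power and Sample Size Calculations expects a linear model to be appropriate, "which we expect to be the case for the primary outcome of total AUDIT scores". The Secondary Aim hypothesis describes the primary outcomes as covering consequences as well as consumption.

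**Which TLFB measure, and how many.** Aim 1 in the Specific Aims refers to "TLFB drinking frequency reports, including number of drinking days per month, number of drinks per drinking day, and number of binge drinking days". The Measures list is introduced only as examples and is partly different. The Aim 1 hypothesis under Data analyses speaks of "significantly greater reductions in total TLFB drinking frequency reports", and Data Analysis for Aim 1 then treats drinking frequency as one outcome. Data Analysis for Secondary Aim counts three primary outcomes.

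**What counts as success.** General analytic approach says "Hypotheses will be planned a priori, and will be limited to the examination of a limited number of outcomes". No section gives a testing order, an alpha split, or a rule on how many measures must differ.

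**The concern.** The primary outcome decides what the trial may claim. Here the AUDIT and alcohol consequences are each primary in one place and secondary in another, and the TLFB yields several candidate measures with none chosen. Drinking days could fall while drinks per drinking day does not, and nothing in the plan says whether the intervention would then have succeeded.

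The missing rule has different consequences depending on how the gap is filled:

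- With one primary measure, the two-sided error is 5%.
- If any one of three measures suffices at .05, the error exceeds 5%.
- If all three are required, the error is at most 5% but power falls below the stated 80%.

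The background section says the result will settle whether peers should be assigned to this work in VA emergency departments. That decision needs an identifiable primary result.

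**Working it through.** **Inputs from the plan.** 450 randomized, 225 per arm (ED Staffing / Subject Accrual). 80% retained, n = 360, so 180 per arm; two-sided alpha .05; 80% power at d = 0.30 (Power and Sample Size Calculations).

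**Assumptions, because the plan is silent.** The success rule; equal correlations between the three measures; d = 0.30 on each. All figures use the plan's simple two-group basis, not the planned mixed model.

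**Step 1: the plan's own figure.** The expected test statistic is d × √(n/2) = 0.30 × √(180/2) = 2.846. Normal-approximation power is Φ(2.846 − 1.960) = Φ(0.886) = 0.812; the noncentral t gives 0.810. The smallest d detectable with 80% power is 0.296. The stated 80% at d = 0.30 therefore reproduces. Nothing in this calculation is specific to the AUDIT: it holds for any single, roughly normal outcome.

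**Step 2: error if any one of three suffices at .05.** For independent measures, 1 − 0.95³ = 0.143. For correlated measures, numerical integration gives the values in the table.

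**Step 3: Bonferroni, .05/3 = .0167 per measure.** The critical value is 2.394. Power per measure is Φ(2.846 − 2.394) = Φ(0.452) = 0.674; the noncentral t gives 0.670. The d detectable with 80% power rises to 0.342.

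**Step 4: other rules.** With independent measures, all three at .05 gives 0.812³ = 0.536, and at least one at .05/3 gives 1 − (1 − 0.674)³ = 0.965. The remaining power values come from simulation under the normal approximation.

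| Correlation | Error, any of three at .05 | Holm power, per measure | At least one significant (Bonferroni or Holm) | All three at .05 |
|---|---|---|---|---|
| 0 | 14.3% | 77% | 97% | 54% |
| 0.5 | 12.5% | 75% | 88% | 63% |
| 0.8 | 9.8% | 74% | 81% | 70% |
| 0.95 | 7.3% | 72% | 74% | 76% |

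**Step 5: the effect size rationale.** The plan supports d = 0.30 by saying: "This is a relatively modest and reasonable effect size for studies of SBIRT models of alcohol brief interventions". This is a general statement about such interventions. It gives no standard deviation or expected difference for any TLFB measure, so it still has to be confirmed for whichever one is named.

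**The case against.** The strongest reply is that the plan can be read consistently as having three TLFB measures throughout. Aim 1 uses drinking frequency as an umbrella term for three named measures, the mediation analysis counts three, and the single outcome in Data Analysis for Aim 1 may be the same umbrella. On that reading the AUDIT phrase is an editorial slip in the power section. The mention of consequences is a slip in a mediation hypothesis, and the analysis paragraph below it tests only alcohol use.

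The plan also fixes more than it might seem. It sets one time-averaged treatment effect, with the time-by-group interaction in a second model, so three visits need not mean three tests. The inflated error arises only under a rule that no section states. Finally, the power figures above cover only a roughly normal outcome, while the plan allows the model type to change and also gives a Poisson calculation.

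Much of this is fair. The AUDIT wording alone would be editorial, the mention of consequences does not alter the Aim 1 test, and the time-averaged effect is worth keeping. The umbrella reading does not close the gap, however: it leaves three primary measures, each tested at .05, with no statement of how they combine. The Poisson calculation does not close it either, since its example is treatment visits with a control mean of 1, not a drinking measure.

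**Conclusion.** The concern holds and should be corrected before outcomes are examined by arm. The plan does not identify which TLFB measure is primary or what result counts as success, and its linear-model power statement is tied to an outcome it elsewhere calls secondary.

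The arithmetic behind 80% power is sound, and 450 participants remain adequate for one roughly normal primary outcome if d = 0.30 is right for it. With three primaries, the position depends on a rule the plan does not give. Unadjusted any-of-three testing would have an error of about 7% to 14% over correlations 0.95 to 0. Adjusted testing would give 67% power per measure under Bonferroni, or 72% to 77% under Holm. Requiring all three would give 54% to 76% over correlations 0 to 0.95. These figures rest on equal correlations, d = 0.30 on every measure, and a simple two-group comparison.

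**What to change.** Before outcomes are examined by arm, name one TLFB measure, with its time-averaged effect, as the primary outcome and make the others secondary. The choice belongs to the sponsor; drinking days is one option, but the text does not settle it. Replace the AUDIT wording in the power section with that outcome. Confirm that the d = 0.30 rationale and the linear-model expectation apply to it, and re-run the power statement if they do not. Then align Aim 1 in the Specific Aims, the Primary Outcome entry, Data Analysis for Aim 1, and the Secondary Aim hypothesis and analysis.

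If three primaries are kept, state whether any or all must succeed and what adjustment applies, and restate power for that rule from the figures above. Under Bonferroni, for example, 80% power per measure holds at d = 0.34 rather than 0.30.

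The cost is protocol and SAP wording, plus a re-run power statement if three are kept. No extra participants or data are needed. Naming one primary keeps the 80% figure for a roughly normal outcome. Keeping three lowers per-measure and all-three power, although the chance of at least one significant result stays at about 81% or more up to correlation 0.8 and is 74% at 0.95.

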ED Staffing / Subject Accrual. Because it is not possible to staff the project continuously (168 hours/week), this study will use the following sampling frame that has been used successfully in our previous ED research to ensure obtaining a representative sample of Veterans presenting to the AAVA ED. Project staff in the ED will recruit patients for the study 5 days per week between the hours of 10AM to 6PM. The majority of the recruitment time will be spent in the ED between 10AM and 6PM because 65-70% of patients enter the ED during those hours. In addition, another three days/week will include a weighted sampling of recruiting between either 7AM-3PM or 3PM-11PM time period. Thus, a total of 8 shifts (8 hours each) will be staffed each week to recruit, consent, screen patients, conduct baseline assessments, and deliver brief advice. Based on our previous ED studies where we have used similar staffing schedules we expect to accrue the following numbers: 30 months of screening x ~130 patients/month approached = 3,900; it is expected that 80% (n=3,120) will agree to participate and will be screened. We conservatively expect that 15% of the screened patients will have a positive screen and will be randomized (450 randomized; 225 per group). Randomization Procedures. Stratified random assignment to conditions will be by sex and presence of an AUD (yes/no) defined as a score of 14 for men and 10 for women on the AUDIT. Randomization by sex will be used because men and women generally differ in their rates and nature of alcohol use, problems, and outcomes. Random assignment will also be stratified based on meeting criteria for past year AUD (yes/no) because of potential differences in problem severity and potential intervention response. Randomization will proceed in blocks of 10 within study cells, in order to equalize randomization over time. Follow-up staff will be blind to condition. Participants in both conditions will receive written information regarding alcohol and VHA resources and be re-contacted to complete 3-, 6-, and 12-months follow-ups.

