Data Analysis for Aim 2: The focus of Aim 2 is to study intervention effects on secondary outcome of frequency of primary care and mental health specialty care visits (as two separate outcomes) from the TSR, calculated as an average number of visits per month during each follow-up period. Similar to Aim 1, analyses will generally use a mixed effect model framework. As described above, initial analyses will examine the distribution of outcome measures over follow-up in order to select an appropriate model (e.g. Poisson regression or a related method for counts of visits). Our analysis strategy will parallel Aim 1 in terms of the independent variables, *random effect for peer/brief advice, focus on time-average treatment effects, and additional modeling of interactions of group and time.*

Secondary Aim will determine the mediators (e.g., motivation to change, self-efficacy, coping, social support) of the effect of the intervention and linkage on subsequent alcohol use and alcohol-related consequences. **Hypothesis:** The effect of randomization to APM compared to BA on the primary outcomes (i.e., alcohol consumption and consequences) will be mediated by differences between groups in motivation to change, self-efficacy, and perceived helpfulness of peer support.

Data Analysis for Secondary Aim: *In order to establish temporal ordering, we will examine whether level of the hypothesized mediators at 3 and 6 months post-baseline mediates the effect of random assignment on 6- and 12-month measures of the three primary outcomes of alcohol use behaviors.^{90,91} We will first determine the whether study condition is associated with the hypothesized mediators over the first six months of follow-up and check for a direct effect of the mediators at 3 and 6 months on alcohol use as measured at 6- and 12-months follow-up. We will estimate the indirect effect of the intervention on alcohol use through the mediators and conduct significance testing of this effect using macros created by Preacher and Hayes.⁹²*

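### The count-outcome power statement holds at a rate ratio of 1.34, but at 0.75 power falls short of the stated 80% under every standard Poisson method (about 72-78%)

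*Combined protocol and SAP*

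**What the plan says.** The Power and Sample Size Calculations section sets the inputs. On retention, "we expect that at least 80% of participants will be retained (n=360"). On software and test, "All power analyses used G*Power 3.1.9 software and a two-sided" alpha of .05. The section says that partial follow-up data are left out of the calculation, which leaves one count per retained participant. The section ED Staffing / Subject Accrual gives equal allocation, "450 randomized; 225 per group", so 360 retained means 180 per arm.

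For counts the section works from "assuming a mean level in controls of 1 (e.g., an average of 1 alcohol-related treatment visit in a follow-up period") and concludes that "we achieve 80% power to detect an incidence rate ratio of 0.75 or 1.34 under a Poisson framework". It does not say which Poisson procedure was run, and it does not say which group is the reference for the ratio.

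The outcomes that this serves are in Data Analysis for Aim 2: the "secondary outcome of frequency of primary care and mental health specialty care visits (as two separate outcomes"). The Aim 2 hypothesis is that APM participants "will be significantly more likely to engage in primary, specialty care, and other VHA supportive services", which is a ratio above 1 for APM relative to BA.

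**The concern.** With the control mean fixed at 1, a ratio below 1 produces fewer events than its reciprocal above 1. The expected totals are 180 × (1 + 0.75) = 315 events at 0.75 and 180 × (1 + 1.34) = 421 at 1.34. The two ratios are almost the same distance from 1 on the log scale (0.288 and 0.293), so one would expect less power at 0.75 than at 1.34 unless the variance in the calculation ignores the active-arm rate. Giving both the same 80% therefore needs checking.

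What is at stake is the accuracy of one printed detectable effect. A reader who relies on 0.75 would credit the trial with slightly more ability to detect a fall in visits than its own inputs give.

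**Working it through.** **Inputs.** N = 360 in total, 180 per arm; control mean 1; two-sided alpha .05 (z = 1.96); Poisson; RR = APM mean divided by BA mean. The procedure is not stated, so several standard ones are shown.

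**Formulas.** Multiplied by N, the variance of the log rate ratio is:
- under the alternative, V1 = 2 + 2/RR;
- under the null with both arms at the control rate, V0 = 4;
- under the null with both arms at the average rate, Vp = 8/(1 + RR).

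Power is then:
- Signorini: Φ[(√N·|ln RR| − 1.96·√V0)/√V1]
- Null variance in both terms: Φ[(√N·|ln RR| − 1.96·√V0)/√V0]
- Wald: Φ[√N·|ln RR|/√V1 − 1.96]
- Pooled-null: Φ[(√N·|ln RR| − 1.96·√Vp)/√V1]

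**The plan's upper figure, RR = 1.34.** √360 × ln 1.34 = 18.974 × 0.29267 = 5.553; √V1 = 1.869; √Vp = 1.849.
- Signorini: (5.553 − 3.920)/1.869 = 0.874, power 80.9%
- Null variance: (5.553 − 3.920)/2 = 0.817, power 79.3%
- Wald: 5.553/1.869 − 1.96 = 1.011, power 84.4%
- Pooled-null: (5.553 − 1.96 × 1.849)/1.869 = 1.032, power 84.9%

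The first two reproduce 80% at 1.34. The other two exceed it.

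**The plan's lower figure, RR = 0.75.** √360 × |ln 0.75| = 18.974 × 0.28768 = 5.458; √V1 = 2.160; √Vp = 2.138.
- Signorini: (5.458 − 3.920)/2.160 = 0.712, power 76.2%
- Null variance: (5.458 − 3.920)/2 = 0.769, power 77.9%
- Wald: 5.458/2.160 − 1.96 = 0.567, power 71.5%
- Pooled-null: (5.458 − 1.96 × 2.138)/2.160 = 0.587, power 72.1%

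**Check without these approximations.** Full enumeration of the Wald, score and likelihood-ratio tests with 180 per arm gives 71.8-72.0% at 0.75 and 84.7-84.8% at 1.34. Simulation of the Wald test gives about 72% at 0.75. The exact conditional test gives 70.0% and 83.7%.

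**Ratios that do have 80% power, and the total N needed at 0.75:**

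| Method | Lower ratio | Upper ratio | N for 80% at 0.75 |
|---|---|---|---|
| Signorini | 0.739 | 1.336 | 398 |
| Null variance | 0.744 | 1.344 | 380 |
| Wald | 0.725 | 1.319 | 443 |
| Pooled-null | 0.727 | 1.317 | 437 |

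The first two pairs print as 0.74 and 1.34, the last two as 0.72-0.73 and 1.32. None prints as 0.75 and 1.34.

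**Does ignoring dropout explain the pair?** No. At N = 450, the same four forms give 81-86% at 0.75 but 87-92% at 1.34.

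**The case against.** The strongest objection is rounding. Printed to two decimals, 0.75 covers values from 0.745. Under the null-variance form, power at 0.745 is 79.7%. The reciprocal of 1.34, which is 0.746, has the same 79.3% as 1.34 itself, because that form is symmetric on the log scale. An author who solved for 1.34 and printed its mirror image would write exactly this pair. This stands in part: under that one form the gap is close to rounding. It does not remove the point. The 80% solution there is 0.744, which prints as 0.74, and 0.745 stays below 80% under all four formulas (77.9% Signorini, 73.3% Wald, 73.9% pooled-null).

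Second, the sentence names no reference group. If 0.75 were BA relative to APM, with the APM mean at 1.333, Signorini power would be 79.5%. But the sentence fixes the control mean and offers two ratios joined by *or*, and General analytic approach justifies two-sided tests by the possibility that APM does worse. Two directions is the natural reading. The ambiguity is still a reason to name the reference group.

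Third, the procedure is unknown and the control mean is a round illustration; a mean of 1.05-1.11 would restore 80% at 0.75 under the two forms that match 1.34. That is true. It limits how precisely the shortfall can be stated, but not its presence on the inputs printed.

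A reader might also infer that 0.75 was obtained by inverting the upper solution (1/1.336 = 0.749). That fits the numbers, but the document does not say how the figure was derived.

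**Conclusion.** Wrong as written, and minor. On the plan's own inputs, the claim of 80% power at 0.75 is not met by any standard method tried. The shortfall is 2-4 percentage points under the approximations that reproduce 1.34 and about 8 points under Wald, pooled-null and simulation. In terms of the ratio, it is 0.006-0.011 under the former and 0.023-0.025 under the latter. The 1.34 figure stands. This rests on 180 analysed per arm, a control mean of exactly 1, one Poisson count per participant, and the ratio read as APM relative to BA.

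Two stronger readings are not supported. A reader might infer that the trial is underpowered for Aim 2 or that its sample size is wrong. The hypothesised direction for service use is above 1, where the statement holds, and the separate claim for a standardised difference of 0.30 reproduces at about 81% with 180 per arm. A reader might also infer that 0.74 is simply the right value. It reaches about 80% only under the two approximations that match 1.34; simulated power at 0.74 is about 75%.

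**What to change.** In the Power and Sample Size Calculations section, name the Poisson procedure used in G*Power, state that the ratio is APM relative to BA, and give both 80% ratios from that one procedure:
- 0.74 and 1.34 if it was Signorini or null variance; or
- about 0.72-0.73 and 1.32 if it was Wald or pooled-null, which the simulation supports.

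Alternatively, keep 0.75 and state its power as about 72-78%, depending on method.

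The cost is one rewritten sentence. The stated detectable ratio below 1 becomes slightly less favourable. Sample size, design and analysis stay as they are.
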